1.8.3 Safety Analysis

This is an epidemiological study. No safety data were to be collected.

1.9 Deviations from the Analysis Foreseen in the Protocol

The protocol foresaw an exploratory analysis of the outcome variable using a penalized hierarchical logistic regression model for discrete choices.

Since a penalized logistic regression is not available in SAS, it was decided to use the classical multinomial logistic regression approach, with a stepwise selection procedure.

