9.1 Statistical Methods

The statistical analysis will be performed using SAS software 9.2.

9.1.1 Primary Objective(s): Calculation of Epidemiological Measure(s) of Interest (e.g. descriptive statistics, hazard ratios, incidence rates, test/retest reliability)

Systemic treatment choices and best supportive care are defined as :

- 1) Chemotherapy (chemo)
- 2) Immunotherapy (IO)
- 3) immuno combined therapies (IO+IO)
- 4) IO+chemo
- 5) IO+bevacizumab+chemo (IO+bev+chemo)
- 6) best supportive care (BSC).

Descriptive statistics of the relation between variable category and systemic treatment choice will be provided. The descriptive statistics will involve the number of times (frequency) a variable category is indicated as being linked to a systemic treatment option.

For each of the variable categories that are linked to a systemic treatment choice, descriptive statistics of the underlying variables will be provided. These descriptive statistics will consist of:

- For the quantitative variables, summary statistics including mean, standard deviation, 95% confidence interval on the mean, minimum, first quartile, median, third quartile, maximum, and number of available and number of missing observations.
- For the categorical variables, frequencies and percentages.

In an exploratory analysis, a penalized hierarchical logistic regression model for discrete choices will be used to evaluate the effect of the potential explanatory variables on the 1st line systemic treatment.

9.1.2 Secondary Objective(s): Calculation of Epidemiological Measure(s) of Interest (e.g. hazard ratios, incidence rates, test/retest reliability)

No secondary objectives.

9.1.3 Exploratory Objective(s): Calculation of Epidemiological Measure(s) of Interest (e.g. hazard ratios, incidence rates, test/retest reliability)

Investigate if there are differences in the link between variable categories and systemic treatment choices for the 4 types of sites that are defined.

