1.2.2 Endpoints

The outcome variable is systemic treatment choice or best supportive care, defined as:

1. Chemotherapy (chemo)
2. Immunotherapy (IO)
3. Immuno combined therapies (IO+IO)
4. IO+chemo
5. IO+bevacizumab+chemo (IO+bev+chemo)
6. Best supportive care (BSC)

In practice, only four categories of the outcome variable were observed: Chemo, IO, IO+chemo, and BSC. Therefore, in the analysis the outcome variable will be considered as having four levels.

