1.3 Study Design

This is a multicenter non-interventional cross-sectional study on first-line systemic treatment choice in stage IV NSCLC patients coming to the consultation. The study was to involve approximately 21 Belgian hospitals where consecutive patients with metastatic stage IV NSCLC selected for systemic

treatment or BSC are included in the trial at the time the patient signs the informed consent form (ICF). Patients selected for systemic treatment, should have received at least their first dose and a maximum of one cycle of the same treatment.

The pneumo-oncologist who treats the patient fills in the CRF, indicating the systemic treatment or BSC option and the link with the variables that impact the choice of systemic treatment or BSC. The actual value of the considered variables is also recorded in the CRF.

A questionnaire must be filled in characterizing the site and allowing the site to be assigned to a group based on the number of newly diagnosed patients per year with lung cancer (diagnostic volume) and whether the site participates in interventional clinical trials (CT participation).

In order to minimize bias, it was emphasized to the participating centers that consecutive patients need to be included in the study. In addition, a maximum of 10% (20 patients) of the total study population can be enrolled per site.

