1.8.2 Statistical Modelling

An exploratory analysis will be performed, consisting of a multinomial logistic regression model that assesses the effect of patient characteristics and the site type on the outcome variable.

The previously defined outcome variable has four levels (chemo, IO, IO+chemo and BSC). The level with the highest frequency will be used as the reference in the multinomial logistic model.

Variables considered as predictors in the model are the site type and patient characteristics with less than 20% missing or unknown values. In case of yes/no variables with further conditional questioning (e.g. Inflammatory interstitial lung disease (yes/no) and if yes, Active/non-active) only the yes/no variable is included in the model. Selection of the final model, containing only predictors with a significant effect on the outcome variable, will be done using automatic selection procedures.

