2.5 Exploratory Analysis

The following variables will be considered in a multinomial stepwise logistic regression analysis:

- Site type (4 subgroups)
- Age
- Gender
- Weight loss
- Smoking status (current/former (≥ 1 year)/never)
- ECOG status (0/1/2/3-4)
- Patients' preference for treatment choice (yes/no)
- Metastatic disease status (M1a/M1b/M1c)
- Tumor size diameter
- Number of metastatic sites
- Brainmets (yes/no)
- Livermets (present/not present)
- Concomitant malignancies (present/not present)
- Histology (squamous/non-squamous)
- IHC PD-L1 (PD-L1 TPS $<1\%$ / $1-49\%$ / $\geq 50\%$)
- High TMB (present/not present)
- Genetic testing complications (turn-around time/biopsy availability)
- Each co-morbidity (yes/no)
- Each auto-immune disease (yes/no)
- Use of corticosteroids, other immunosuppressants, and antibiotics (yes/no)
- Use of each prior cancer treatment in earlier stage NSCLC (yes/no)

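### SAP 1.9 drops the protocol's hierarchical structure without a reason; site type is then tested with no allowance for site, inside a stepwise search too large for the sample

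*SAP*

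**What the plan says.** Protocol 9.1.1 states that, as an exploratory analysis, "a penalized hierarchical logistic regression model for discrete choices will be used to evaluate the effect" of the explanatory variables on first-line treatment. It does not define the hierarchy.

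SAP 1.9 repeats both features of that model and then departs from it. The reason is "Since a penalized logistic regression is not available in SAS", and the result is that "it was decided to use the classical multinomial logistic regression approach, with a stepwise selection procedure".

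SAP 1.8.2 describes "a multinomial logistic regression model that assesses the effect of patient characteristics and the site type on the outcome variable". It also says: "Selection of the final model, containing only predictors with a significant effect on the outcome variable, will be done using automatic selection procedures". SAP 2.5 lists the candidates, with site type (four groups) first. SAP 1.6 defines site type from two hospital-level facts, diagnostic volume and trial participation, so all patients of a hospital share one value.

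The outcome has four levels because "only four categories of the outcome variable were observed: Chemo, IO, IO+chemo, and BSC". SAP 1.3 gives about 21 hospitals; SAP 1.4 gives 200 to 210 patients and no formal sample size calculation.

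**The concern.** Two features were planned and both were dropped, but the stated reason covers only one. The lack of a penalised procedure says nothing about whether a hierarchical structure could be kept.

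The gap matters most for site type. Patients of one hospital share its protocols, tumour board and testing access, so their treatments may be alike for reasons unrelated to volume or trial participation. A model with no site term counts about 200 patients as independent evidence on a factor that varies over only about 21 units. The primary objective names site characteristics, Protocol 9.1.3 adds a comparison of the four site types, and this is the only multivariable analysis. A hospital habit could be reported as an effect of site type.

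The second stake is the list of selected predictors. The final model keeps only significant terms, so readers will take it as the list of what drives treatment choice. If the search is too large for the data, a repeat of the study would give a different list.

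**Working it through.** The plan gives no alpha, power or model-size figure for this analysis, so there is none to reproduce.

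**1. The two models compared.** Protocol: penalised, hierarchical. SAP: unpenalised, no hierarchical term, stepwise. Reason given for losing penalisation: software. Reason given for losing the hierarchy: none.

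**2. Size of the search (counted from SAP 2.5).**
- Listed singly: 17 terms. Their df in list order: 3+1+1+1+2+3+1+2+1+1+1+1+1+1+2+1+1 = 24.
- Yes/no groups: 13 co-morbidities + 5 autoimmune diseases + 3 medications + 4 prior treatments = 25 terms, 25 df.
- Total: 17 + 25 = 42 terms; 24 + 25 = 49 df. Four outcome levels give three logits, so 49 × 3 = 147 slopes.
- Patients per slope: 200/147 = 1.36 to 210/147 = 1.43.
- Smallest outcome level: at most 210/4 = 52.5, so 52 patients; 52/49 = 1.06 per candidate df.
- If the missingness filter removed tumour mutational burden and genetic-testing complications (an assumption), 47 df and 141 slopes would remain.

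**3. Site-type test ignoring site (3 df × 3 logits = 9 df).** The documents give no ICC, so a range is assumed. With m = 210/21 = 10 patients per site, the design effect is DE = 1 + (m − 1) × ICC, and the approximate true size of a nominal 5% test is P(χ²₉ > 16.92/DE).

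| ICC | DE | 210/DE | Size from formula |
|---|---|---|---|
| 0.01 | 1.09 | 193 | 8% |
| 0.05 | 1.45 | 145 | 23% |
| 0.10 | 1.90 | 111 | 45% |

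Simulations of 21 sites of 10, with assumed outcome shares and site-type splits:
- ICC on the observed scale (correlation of the treatment indicators themselves): 8-10%, 26-28% and 46-49% at 0.01, 0.05 and 0.10; about 6% with no clustering.
- ICC on the latent logit scale, SD²/(SD² + 3.29): 14-17% at 0.05 and 25-30% at 0.10; 5-7% with no clustering. The same number means weaker clustering on this scale, so any quoted ICC needs its scale.

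**4. Site type under the full stepwise rule** (assumed 5% entry and removal, 205 patients, 40 candidates): falsely selected in 1-4% of runs with no clustering, 6-9% at ICC 0.04-0.05 and 18% at about 0.10.

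**5. Stability of the selection.**
- No true predictors, 5% entry: 42 × 0.05 = 2.1 false entries expected. P(at least one) = 1 − 0.95⁴² = 0.88 if independent. A forward-selection simulation gave a mean of 2.1 and 0.84.
- With a removal step and two to four true predictors (PD-L1 and histology, with or without ECOG and age): 13-40% of selected terms were false, and 32-58% of runs had at least one. Histology was kept in 30-46% of runs at an odds ratio of 2.7, 71-75% at 4 and 92-97% at 6.

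**6. Remedies tried on simulated data.** Permuting site type over sites gave 3-7% false positives. A Dirichlet-multinomial test allowing for site gave 9% and 12% at ICC 0.05 and 0.10 (120 runs). It stands in for a random intercept per logit and is not that model.

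Monte Carlo error is 1-3 percentage points, or 3-6 for runs of 150 or fewer.

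**The case against.** The strongest reply is that the model is labelled exploratory, the change is disclosed, and the descriptive analysis of the primary objective does not depend on it. All of that stands and limits the weight of the point.

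Safeguards also exist. Predictors with 20% or more missing are excluded, conditional items are reduced to yes/no, the outcome has only its observed levels, and each site is capped. It would be wrong to say the SAP offers no protection. None of these, however, allows for site or brings the candidate list near what the sample supports.

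The high false-positive rates in step 3 belong to a single test, whereas the SAP plans stepwise selection, for which step 4 is closer. In addition, a covariate-adjusted version of the single test already rejected in 11% of runs with no clustering, so part of any excess is small-sample error. Both points stand.

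Some stronger readings are tempting but unsupported:
- *That the protocol's hierarchy certainly meant patients within sites.* It is undefined and could mean nested treatment choices. The clustering point does not need it, because site type is a hospital-level factor either way.
- *That the SAP declares patients independent.* It does not; this follows from a classical model with nothing stated for site.
- *That the cap shows heavier clustering.* SAP 1.3 says "a maximum of 10% (20 patients) of the total study population can be enrolled per site", but 21 × 20 = 420 exceeds 210, so 20 cannot be the typical site size.
- *That penalisation must be restored.* A ridge fit with site intercepts was closer to the true log-odds than stepwise in only 40-62% of simulated runs.
- *That the protocol's minimum of 30 patients should screen predictors.* It is a subgroup rule and could remove a site type holding two or three hospitals.
- *That the model was changed because of the results.* The SAP shows only that the observed treatment categories were known.

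**Conclusion.** The point holds and should be fixed. From the documents alone, the hierarchical structure is dropped without explanation, site type is tested with no allowance for site, and up to 42 terms and 147 slopes are searched on 200-210 patients.

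The size of the clustering error depends on an ICC the documents do not give. For the single test it is slight at 0.01, and roughly three to five times the nominal 5% at 0.05, depending on the scale. Under the stepwise rule, false selection of site type is modest at 0.04-0.05 and becomes a real problem near 0.10. Outcome shares, prevalences, effect sizes and selection levels were also assumed, so the percentages are illustrations, not forecasts. The consequence is an unreliable site-type result and an unstable list of predictors in an exploratory model. It does not invalidate the study's descriptive results.

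**What to change.** In SAP 1.8.2 and 2.5:
1. Account for site when testing site type, by a random site intercept for each logit or a cluster-robust variance. Because some site types may hold few hospitals, check the p-value by permuting site type over sites.
2. Alongside the selected model, report how often each candidate is selected in a bootstrap that resamples sites within site type.

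In SAP 1.9:

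3. State what the hierarchical structure was meant to be and, if it is not restored, why it was dropped.

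A penalised fit in other software is an option, not a requirement; if used, record the departure from SAS 9.2.

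The cost is SAP wording, some extra programming and wider intervals for site type. No new data are needed.

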2. DETAILS OF THE STATISTICAL ANALYSIS

2.1 Sample Description

- Number of subjects enrolled, and number in the EP, overall and broken down by site
- First and last inclusion date, overall and by site

2.2 Site Characteristics

- Descriptive statistics for diagnostic volume
- Frequency distribution and 95% CI for CT participation
- Frequency distribution for site type
- Frequency distribution for Genetic testing, in-house
- Frequency distribution for Genetic testing, Referral testing
- Frequency distribution for PD-L1 IHC, in-house
- Frequency distribution for PD-L1 IHC, Referral testing
- Frequency distribution for NGS testing, in-house (yes/no) and frequency distribution for Type
- Frequency distribution for NGS testing, Referral testing (yes/no) and frequency distribution for Type

2.3 Patient Characteristics by Outcome Variable and by Site Type

- Frequency distribution and 95% CI for the outcome variable (treatment choice).
- Frequency distributions and 95% CI for the outcome variable (treatment choice) by site type.

The following descriptive analysis is performed broken down by the outcome variable (all patients in the EP and 4 subgroups), and by site type (4 subgroups):

Demographic data

- Descriptive statistics for Age and Weight loss
- Frequency distributions for Gender, Smoking status, and ECOG
- Frequency distribution for Patients' preference for treatment choice

Medical history

- Frequency distribution for Metastatic disease status
- Descriptive statistics for Tumor size diameter and Number of metastatic sites
- Frequency distributions for Brainmets, Symptomatic/asymptomatic, and Treatment
- Frequency distributions for Livermets, Concomitant malignancies, Histology, IHC PD-L1, High TMB, and Genetic testing complications

Co-morbidities

- Frequency distribution for each Co-morbidity

Auto-immune disease

- Frequency distributions of presence and activity of each Auto-immune disease

Current/recent medication

- Frequency distributions for use of Corticosteroids and for Dose
- Frequency distributions for use of Other immunosuppressants and Antibiotics

Prior cancer treatment in earlier stage NSCLC

- Frequency distribution for each Prior cancer treatment in earlier stage NSCLC

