3.2 Study Population

210 eligible stage IV NSCLC subjects treated in approximately 21 Belgian hospitals starting first-line treatment or best supportive care will be enrolled in line with inclusion and exclusion criteria. The estimated recruitment period to reach the target of 210 eligible patients is 5 months. Upon inclusion of 210 eligible patients the recruitment will be closed. Only a maximum of 10% of subjects can be enrolled by one site.

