9.3 Sample Size and Power Calculations

The study is descriptive and no sample size calculations will be performed. In order to have a representative picture of the pneumo-oncologists' NSCLC systemic treatment decision in Belgium, a minimum of 200 patients need to be enrolled in the study.

A maximum of 10% of the total study population can be enrolled in a site to avoid bias. A minimum of 30 patients need to be included in a subgroup for any given analysis.

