1.4 Sample Size Justification

No formal sample size calculation was performed. The protocol states that a maximum of 210 eligible patients and a minimum of 200 patients are to be included to have a representative picture of the pneumo-oncologists' NSCLC systemic treatment decision in Belgium.

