1.8.1 Descriptive Analysis

Throughout this document the following terminology is used for indicating the type of descriptive analysis:

- 'Descriptive statistics' is the description to be provided for quantitative variables, and consists of the mean, standard deviation (SD), 95% confidence interval (CI) on the mean, minimum, 1st quartile, median, 3rd quartile, maximum, number of available observations, and number of missing observations.
- 'Frequency distribution' is the description to be provided for ordinal and nominal variables and consists of numbers and percentages for each of the scores or categories. Exact 95% CIs will be provided for key variables.

The descriptive analysis consists of:

1. Site Characteristics

Descriptive statistics will be provided for the diagnostic volume. Other site characteristics, including the site type, will be described by frequency distributions.

2. Patient Characteristics by Outcome Variable and by Site Type

Descriptive statistics and frequency distributions will be used to describe numerical and ordinal/nominal patient characteristics, respectively. The analysis will be performed for:

- All patients in the EP
- By outcome variable (Chemo+IO, Chemo, IO, BSC)
- By site type (4 subgroups).

Also, frequency distributions of the outcome variable will be given for all patients in the EP and by site type.

3. Impact of Covariates on the Outcome Variable

The impact of variables, as indicated by the investigator, on the outcome variable, is described as one of the following:

- Important impact (variable selected as one of the three most important characteristics)
- Impact (variable indicated as having an impact, but not selected among the three most important characteristics)
- No impact (variable not indicated as having impacted the treatment choice)

For each variable the frequency distribution of the impact is provided per level of the outcome variable (chemo, IO, IO+chemo, and BSC).

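### The 95% CIs for the treatment shares make no allowance for clustering in about 21 hospitals, and will be too narrow as statements about Belgium if choice varies between hospitals

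*SAP*

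**What the plan says.** SAP 2.3 lists "Frequency distribution and 95% CI for the outcome variable (treatment choice" and then "Frequency distributions and 95% CI for the outcome variable (treatment choice) by site type". SAP 1.8.1 sets the type of interval: "Exact 95% CIs will be provided for key variables". It names no formula. A single-sample binomial (Clopper-Pearson) interval is the natural reading of an exact CI on one proportion, but that is an inference. SAP 1.8.1 also puts a 95% CI on the mean of every quantitative variable.

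The patients come from a limited number of hospitals: "210 eligible stage IV NSCLC subjects treated in approximately 21 Belgian hospitals" (Protocol 3.2), and "a maximum of 10% (20 patients) of the total study population can be enrolled per site" (SAP 1.3). Protocol 9.3 says "a minimum of 200 patients need to be enrolled in the study", and gives the reason: "In order to have a representative picture of the pneumo-oncologists' NSCLC systemic treatment decision in Belgium".

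Neither document describes a design effect, a cluster-robust or survey variance, or a random site effect for these intervals. Consecutive inclusion and the 10% cap are presented as controls on bias (Protocol 9.2.1, SAP 1.3). The only hierarchical method was the exploratory regression in Protocol 9.1.1. SAP 1.9 replaces it with a classical multinomial model, and either model would leave the descriptive intervals unchanged.

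**The concern.** A plain exact interval has its stated coverage only if the 200 to 210 choices are independent. Here the choice is the treating physician's, and each hospital contributes about ten patients on average. The study itself hypothesises that site characteristics relate to treatment choice (Protocol 2.1, SAP 1.2.1), and it records in-house against referral PD-L1 and NGS testing as site attributes (SAP 1.5.1). A positive ICC is therefore plausible. Differences in case mix between hospitals would add to it, because the shares are unadjusted.

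At stake is the stated precision of the shares; the point estimates are unaffected. With a material ICC, a reader would take the picture of Belgian practice, and the contrasts between site types, as firmer than about 21 hospitals can make them. The intervals on patient-level means such as age and weight loss have the same weakness.

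**Working it through.** The plan offers no precision figure to reproduce: "No formal sample size calculation was performed" (SAP 1.4).

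**Inputs from the documents.** N = 210 in 21 sites, so a mean of 210/21 = 10 per site (Protocol 3.2). The cap is 20 per site (SAP 1.3), which is 10% of the minimum of 200.

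**Assumptions, not in the documents.** ICC 0 to 0.10; true shares 10% to 50%; three enrolment layouts, each 21 sites and 210 patients:
- Equal: 10 per site.
- Uneven A: five sites of 20, three of 14, two of 10, five of 6, six of 3.
- Uneven B: five of 20, three of 15, three of 10, eight of 4, one of 2, one of 1.

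**Formulas.** DEFF = 1 + (m_w - 1) x ICC, with m_w = sum(m^2)/sum(m). Effective n = N/DEFF.
- Equal: m_w = 10.
- Uneven A: m_w = 3022/210 = 14.4.
- Uneven B: m_w = 3108/210 = 14.8.

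Example at ICC 0.05: the equal layout gives DEFF = 1 + 9 x 0.05 = 1.45 and effective n = 210/1.45 = 145. Uneven B gives DEFF = 1 + 13.8 x 0.05 = 1.69 and effective n = 124.

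**Overall share, 40% assumed.** Coverage of the plain exact interval is from 40,000 beta-binomial simulations per setting. The adjusted interval is Clopper-Pearson at effective n with DEFF known. Each cell shows equal / uneven B.

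| ICC | DEFF | Interval at effective n (%) | Coverage of plain exact CI (%) |
|---|---|---|---|
| 0 | 1 / 1 | 33.3-47.0 / 33.3-47.0 | 95.9 / 96.0 |
| 0.01 | 1.09 / 1.14 | 33.0-47.3 / 32.9-47.5 | 95.0 / 94.4 |
| 0.02 | 1.18 / 1.28 | 32.7-47.6 / 32.5-47.9 | 94.0 / 93.0 |
| 0.05 | 1.45 / 1.69 | 32.0-48.5 / 31.3-49.2 | 91.0 / 88.4 |
| 0.10 | 1.90 / 2.38 | 30.8-49.8 / 29.7-51.0 | 86.1 / 81.7 |

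Shares of 10%, 25% and 50% move the coverage at ICC 0.01 to 0.10 by at most about 1.2 points. Uneven A at ICC 0.05 gives 88.3% to 89.4% for shares of 10% to 45%.

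**By site type.** For an assumed type with three sites of 10 (30 patients, the minimum subgroup in Protocol 9.3) and a 40% share, coverage is 96.0% at ICC 0, 91.5% at 0.05 and 86.0% at 0.10.

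**Why one pooled DEFF does not serve the site types.** SAP 1.6 splits sites partly by volume, and DEFF depends on cluster size. For illustration, suppose enrolment follows volume in uneven A, at ICC 0.05:
- Ten largest sites: m_w = 2788/162 = 17.2, DEFF = 1 + 16.2 x 0.05 = 1.81.
- Eleven smallest: m_w = 234/48 = 4.9, DEFF = 1 + 3.9 x 0.05 = 1.19.
- Pooled: DEFF = 1 + 13.4 x 0.05 = 1.67, too small for the first group and too large for the second.

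A pooled DEFF also absorbs real differences between types. With no clustering within types and shares of 50% and 25%, the mean estimated DEFF was about 1.3.

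**Does a clustered interval repair the overall share?** With DEFF estimated from the data (20,000 replicates; equal and uneven A; ICC 0 to 0.10; shares 10% to 45%), the effective-n interval covered 94.4% to 97.4%. At a 30% share, ICC 0.05 and uneven A, the mean half-width was 8.6 points against 6.4 for the plain interval: 8.6/6.4 = 1.34.

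**The case against.** A reader might infer three stronger things that the documents do not support.

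- *That the intervals are too narrow as a matter of fact.* This depends on an ICC that the documents do not give. The exact interval is slightly conservative, so coverage stays near 95% at ICC 0.01. Protocol 1.1 says first-line choice rests on histology, genetic aberrations and PD-L1, which are patient-level drivers. The number of physicians per hospital is not stated. The conditional wording is the right one.
- *That the treatment shares are the primary or headline result.* The primary objective is the relation between characteristics and choice, and Protocol 9.1.1 asks for no CI on the shares. SAP 1.2.2 does, however, make treatment choice the sole outcome variable.
- *That these are the only estimates with a 95% CI.* Patient-level means (SAP 1.8.1) and CT participation (SAP 2.2) have one too.

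It can also be said that the study is descriptive, that no test compares shares in these tables, and that the plain interval is not wrong in this way if inference is confined to the participating hospitals as fixed sites. That is correct, but the plan states no such restriction and gives a Belgian aim for its sample size. Finally, the hospitals are not described as a random sample, so a clustered interval does not by itself secure national inference. That limit stands.

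**Conclusion.** The point holds in conditional form. The planned exact intervals carry no allowance for hospital clustering, and as statements about Belgium they will be too narrow if choice varies between hospitals. With 210 patients in 21 sites the shortfall is negligible at an assumed ICC of 0.01 and small at 0.02. At 0.05 the non-coverage is about 9-12% instead of 5%, and at 0.10 about 14-18% (40% share, equal sites to uneven B). These sizes rest on assumed ICCs, shares and enrolment splits. The by-site-type intervals and the intervals on patient-level means share the weakness. It is worth correcting because the remedy is cheap and uses the observed data, so no ICC need be guessed.

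**What to change.** Amend SAP 1.8.1 and 2.3 as follows.

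1. **Overall treatment shares.** Estimate the variance of each share with site as the cluster, using t with the number of sites minus 1 degrees of freedom. Compute the exact interval at n/DEFF, with DEFF not allowed below 1. Report the DEFF and the ICC beside the table.
2. **Patient-level means.** Use the same site-clustered variance for their 95% CIs.
3. **Shares by site type.** Estimate one common within-type ICC, with site nested in site type. Compute each type's DEFF from its own cluster sizes, 1 + (sum(m^2)/sum(m) - 1) x ICC. Where a type holds only a few sites, label the interval as descriptive of those sites.
4. **Site-level items such as CT participation.** Keep the plain exact CI, since the site is the unit.

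Cost: SAP wording and a modest amount of code. No new data are needed, since SAP 2.1 already reports by site. The overall intervals become roughly 25-35% wider at ICC 0.05 and slightly conservative (about 97% coverage) if there is no clustering. The adjustment does not address how the hospitals were selected, and the report should say so.
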